8. STUDY ASSESSMENTS AND PROCEDURES

The investigator (or an appropriate delegate at the investigator site) must obtain a signed and dated ICD before performing any study-specific procedures.

Study procedures and their timing are summarized in the [SoA](#). Protocol waivers or exemptions are not allowed.

Safety issues should be discussed with the sponsor immediately upon occurrence or awareness to determine whether the participant should continue or discontinue study intervention.

Adherence to the study design requirements, including those specified in the [SoA](#), is essential and required for study conduct.

All screening evaluations must be completed and reviewed to confirm that potential participants meet all eligibility criteria. The investigator will maintain a screening log to record details of all participants screened and to confirm eligibility or record reasons for screening failure, as applicable.

Participants will be screened within 28 days prior to administration of the study intervention to confirm that they meet the study population criteria for the study. If the time between screening and dosing exceeds 28 days as a result of unexpected delays (eg, delayed drug shipment), then participants do not require rescreening if the laboratory results obtained prior to first dose administration meet eligibility criteria.

Every effort should be made to ensure that protocol-required tests and procedures are completed as described. However, it is anticipated that from time to time there may be circumstances outside the control of the investigator that may make it unfeasible to perform the test. In these cases, the investigator must take all steps necessary to ensure the safety and well-being of the participant. When a protocol-required test cannot be performed, the investigator will document the reason for the missed test and any corrective and preventive actions that he or she has taken to ensure that required processes are adhered to as soon as possible. The study team must be informed of these incidents in a timely manner.

If an IV catheter is utilized for blood sample collections, ECGs and vital sign assessments (PR and BP) should be collected prior to the insertion of the catheter.

For samples being collected and shipped, detailed collection, processing, storage, and shipment instructions and contact information will be provided to the investigator site prior to initiation of the study.

The total blood sampling volume for individual participants in this study is approximately 260 mL. The actual collection times of blood sampling may change. Additional blood samples may be taken for safety assessments at times specified by Pfizer, provided the total volume taken during the study does not exceed 550 mL during any period of 56 consecutive days.

To prepare for study participation, participants will be instructed on the information in Protocol Section [5.3](#) Lifestyle Considerations and [Section 6.8](#) Concomitant Therapy.

8.1. Efficacy Assessments

Not applicable.

8.2. Safety Assessments

Planned time points for all safety assessments are provided in the [SoA](#). Unscheduled clinical laboratory measurements may be obtained at any time during the study to assess any perceived safety issues.

8.2.1. Physical Examinations

A complete PE will include, at a minimum, head, ears, eyes, nose, mouth, skin, heart and lung examinations, lymph nodes, and gastrointestinal, musculoskeletal, and neurological systems.

A brief physical examination will include, at a minimum, assessments of general appearance, the respiratory and cardiovascular systems, and participant-reported symptoms.

Physical examinations may be conducted by a physician, trained physician's assistant, or nurse practitioner as acceptable according to local regulation.

Height and weight will also be measured and recorded as per the [SoA](#). For measuring weight, a scale with appropriate range and resolution is used and must be placed on a stable, flat surface. Participants must remove shoes, bulky layers of clothing, and jackets so that only light clothing remains. They must also remove the contents of their pockets and remain still during measurement of weight.

Physical examination findings collected during the study will be considered source data and will not be required to be reported, unless otherwise noted. Any untoward physical examination findings that are identified during the active collection period and meet the definition of an AE or SAE ([Appendix 3](#)) must be reported according to the processes in [Sections 8.3.1 to 8.3.3](#).

8.2.2. Vital Signs

Supine BP will be measured with the participant's arm supported at the level of the heart and recorded to the nearest mm Hg after approximately 5 minutes of rest. The same arm (preferably the dominant arm) will be used throughout the study. Participants should be instructed not to speak during measurements.

The same properly sized and calibrated BP cuff will be used to measure BP each time. The use of an automated device for measuring BP and pulse rate is acceptable; however, when done manually, pulse rate will be measured in the brachial/radial artery for at least 30 seconds. When the timing of these measurements coincides with a blood collection, BP and pulse rate should be obtained prior to the nominal time of the blood collection.

Additional collection times, or changes to collection times, of BP and pulse rate will be permitted, as necessary, to ensure appropriate collection of safety data.

8.2.2.1. Respiratory Rate

Respiratory rate will be measured after approximately 5 minutes of rest in a supine position by observing and counting the respirations of the participant for 30 seconds and multiplying by 2. When BP is to be taken at the same time, respiration measurement will be done during the 5 minutes of rest and before BP measurement.

8.2.2.2. Temperature

Temperature will be measured orally. No eating, drinking, or smoking is allowed for 15 minutes prior to the measurement.

8.2.3. Electrocardiograms

Standard 12-lead ECGs utilizing limb leads (with a 10 second rhythm strip) should be collected at times specified in the [SoA](#) section of this protocol using an ECG machine that automatically calculates the heart rate and measures PR, QT, and QTc intervals and QRS complex. Alternative lead placement methodology using torso leads (eg, Mason-Likar) should not be used given the potential risk of discrepancies with ECGs acquired using standard limb lead placement. All scheduled ECGs should be performed after the participant has rested quietly for at least 5 minutes in a supine position.

TriPLICATE 12-lead ECGs will be obtained approximately 2 minutes apart; the average of the triplicate ECG measurements collected will be recorded.

To ensure safety of the participants, a qualified individual at the investigator site will make comparisons to baseline measurements. Additional ECG monitoring will occur if a) a post dose QTcF interval is increased by ≥ 60 msec from the baseline **and** is > 450 msec; or b) an absolute QT value is ≥ 500 msec for any scheduled ECG. If either of these conditions occurs, then 2 additional ECGs will be collected approximately 2 to 4 minutes apart to confirm the original measurement. If the QTc values from these repeated ECGs remain above the threshold value, then a single ECG must be repeated at least hourly until QTc values from 2 successive ECGs fall below the threshold value that triggered the repeat measurement.

If a) a post dose QTcF interval remains ≥ 60 msec from the baseline **and** is > 450 msec; or b) an absolute QT value is ≥ 500 msec for any scheduled ECG for greater than 4 hours (or sooner, at the discretion of the investigator); or c) QTcF intervals get progressively longer, the participant should undergo continuous ECG monitoring. A cardiologist should be consulted if QTcF intervals do not return to less than the criteria listed above after 8 hours of monitoring (or sooner, at the discretion of the investigator).

In some cases, it may be appropriate to repeat abnormal ECGs to rule out improper lead placement as contributing to the ECG abnormality. It is important that leads be placed in the same positions each time in order to achieve precise ECG recordings. If a machine-read QTc value is prolonged, as defined above, repeat measurements may not be necessary if a qualified medical provider's interpretation determines that the QTcF values are in the acceptable range.

ECG values of potential clinical concern are listed in [Appendix 7](#).

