Diagnostic Assessments:

11. A positive urine drug test.
12. Screening supine BP ≥ 140 mm Hg (systolic) or ≥ 90 mm Hg (diastolic), following at least 5 minutes of supine rest. If BP is ≥ 140 mm Hg (systolic) or ≥ 90 mm Hg (diastolic), the BP should be repeated 2 more times and the average of the 3 BP values should be used to determine the participant's eligibility.
13. Baseline 12-lead ECG (triplicate) that demonstrates clinically relevant abnormalities that may affect participant safety or interpretation of study results (eg, baseline QTcF interval >450 msec, complete LBBB, signs of an acute or indeterminate-age myocardial infarction, ST-T interval changes suggestive of myocardial ischemia, second- or third-degree AV block, or serious bradyarrhythmias or tachyarrhythmias). If the baseline uncorrected QT interval is >450 msec, this interval should be rate-corrected using the Fridericia method and the resulting QTcF should be used for decision making and reporting. If QTcF exceeds 450 msec, or QRS exceeds 120 msec, the ECG should be repeated 2 more times and the average of the 3 QTcF or QRS values should be used to determine the participant's eligibility. Computer-interpreted ECGs should be overread by a physician experienced in reading ECGs before excluding a participant. The average of triplicate measurement should be used for eligibility determination.
14. Participants with ANY of the following abnormalities in clinical laboratory tests at Screening, as assessed by the study-specific laboratory and confirmed by a single repeat test, if deemed necessary:
 - AST or ALT level $> 1.0 \times$ ULN;
 - Total bilirubin level $\geq 1.5 \times$ ULN; participants with a history of Gilbert's syndrome may have direct bilirubin measured and would be eligible for this study provided the direct bilirubin level is \leq ULN.

- eGFR < 81 mL/min/1.73 m² (eg <90 mL/min/1.73 m² with 10% variation) based on the CKD-EPI equation.

Other Exclusions:

15. History of alcohol abuse or binge drinking and/or any other illicit drug use or dependence within 6 months of Screening. Binge drinking is defined as a pattern of 5 (male) and 4 (female) or more alcoholic drinks in about 2 hours. As a general rule, alcohol intake should not exceed 14 units per week (1 unit = 8 ounces (240 mL) beer, 1 ounce (30 mL) of 40% spirit or 3 ounces (90 mL) of wine).
16. Use of tobacco or nicotine containing products in excess of the equivalents of 5 cigarettes per day or 2 chews of tobacco per day.

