7.1.1. ECG Changes

A participant who meets either bulleted criterion based on the average of triplicate ECG readings will be withdrawn from the study intervention.

- QTcF >500 msec.
- Change from baseline: QTcF >60 msec and QTcF >450 msec.

If a clinically significant finding is identified (including, but not limited to, changes from baseline in QTcF after enrollment), the investigator or qualified designee will determine if the participant can continue in the study and if any change in participant management is needed. This review of the ECG printed at the time of collection must be documented. Any new clinically relevant finding should be reported as an AE.

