8.3.3. Follow-Up of AEs and SAEs

After the initial AE or SAE report, the investigator is required to proactively follow each participant at subsequent visits/contacts. For each event, the investigator must pursue and obtain adequate information until resolution, stabilization, the event is otherwise explained, or the participant is lost to follow-up (as defined in [Section 7.3](#)).

In general, follow-up information will include a description of the event in sufficient detail to allow for a complete medical assessment of the case and independent determination of possible causality. Any information relevant to the event, such as concomitant medications and illnesses, must be provided. In the case of a participant death, a summary of available autopsy findings must be submitted as soon as possible to Pfizer Safety.

Further information on follow-up procedures is given in [Appendix 3](#).

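### Section 8.2.3 sets its 500 msec repeat-ECG trigger on uncorrected QT, so read literally it misses a narrow band of participants whom 7.1.1 withdraws for QTcF above 500 msec

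*Protocol*

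**What the plan says.** Protocol 8.2.3 has two escalation steps. The first calls for two further ECGs, and then at least hourly ECGs if the prolongation persists. It is triggered by (a) a QTcF rise of at least 60 msec from baseline with QTcF above 450 msec, or (b) "an absolute QT value is ≥ 500 msec for any scheduled ECG". The second step, continuous monitoring, repeats (a) and (b) with a four-hour persistence condition and adds a third route: "c) QTcF intervals get progressively longer, the participant should undergo continuous ECG monitoring".

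The rest of the section works on corrected intervals:

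- Hourly ECGs continue "until QTc values from 2 successive ECGs fall below the threshold value that triggered the repeat measurement".
- Referral to a cardiologist depends on QTcF.
- The closing paragraph begins "If a machine-read QTc value is prolonged, as defined above", which treats the thresholds as QTc thresholds.

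Elsewhere, 7.1.1 withdraws a participant whose triplicate average shows "QTcF >500 msec", or a QTcF rise of more than 60 msec with QTcF above 450 msec. Appendix 7 and SAP Table 2 also put the 500 msec limit on QTcF. Exclusion criterion 13 gives "baseline QTcF interval >450 msec" as an example of a disqualifying finding, and says that a long uncorrected QT must be rate-corrected before a decision is made on it.

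**The concern.** A monitoring trigger should fire no later than the withdrawal rule it supports. The change-from-baseline pair is in that order: at least 60 msec for monitoring, more than 60 msec for withdrawal. The absolute pair is not, because monitoring is on QT and withdrawal is on QTcF, and the two are equal only at 60 bpm. Above that rate QTcF exceeds QT, so a participant can meet the withdrawal limit while uncorrected QT is well under 500 msec.

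At stake are the two mandatory confirmatory ECGs and the hourly series that follows from them, for someone who has just met the absolute QTcF withdrawal limit. Section 7.1 adds that a participant permanently taken off study intervention does not stay in the study for further evaluation, so monitoring at that moment should be mandatory and not discretionary. Below 60 bpm the literal rule errs the other way and triggers repeats at QTcF values under 500 msec.

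**Working it through.** **Inputs.** Monitoring triggers (a) and (b) from Protocol 8.2.3; withdrawal rule from 7.1.1; entry limit of 450 msec on baseline QTcF from 5.2, criterion 13; Fridericia formula from SAP 6.2.4. The documents give no heart-rate distribution, so 45 to 100 bpm is assumed for the enumeration in step 5. The plan states no figure of its own to reproduce here.

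**Formula.** QTcF = QT / (60/HR)^(1/3), so QT = QTcF × (60/HR)^(1/3).

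**Step 1: when literal (b) misses QTcF above 500.** It misses when QT < 500, that is, when HR > 60 × (QTcF/500)^3. This is a lower bound on heart rate.

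| QTcF (msec) | (b) missed at heart rates above (bpm) |
|---|---|
| 500 | 60.0 |
| 503 | 61.1 |
| 505 | 61.8 |
| 510 | 63.7 |

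**Step 2: when (a) also misses.** It misses when QTcF − baseline < 60. The upper end of the band is therefore baseline + 60.

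| Baseline QTcF (msec) | Band of post-dose QTcF missed by (a) but above 500 |
|---|---|
| 440 | empty (upper end 500) |
| 445 | above 500, below 505 |
| 450 | above 500, below 510 |

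From QTcF 510 upward, (a) fires for every participant with baseline 450 or less.

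**Step 3: one case.** Baseline 445, post-dose QTcF 503, heart rate 80 bpm.

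- Rise = 503 − 445 = 58 msec, so (a) does not fire.
- QT = 503 × (60/80)^(1/3) = 457 msec, so (b) does not fire.
- QTcF 503 > 500, so 7.1.1 requires withdrawal.

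**Step 4: the other direction.** QTcF when QT is exactly 500 msec:

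| Heart rate (bpm) | QTcF (msec) |
|---|---|
| 45 | 454.3 |
| 50 | 470.5 |
| 55 | 485.7 |
| 58 | 494.4 |

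So a participant at 50 bpm with QTcF 470.5 triggers repeats, while one at 80 bpm with QTcF 503 and baseline 445 does not. The 50 bpm participant's repeats are then judged on QTc, which was never above 500.

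**Step 5: enumeration in whole msec and bpm.** With baseline at most 450 and heart rate 45 to 100 bpm, the combinations that require withdrawal but fire neither trigger have baseline 442 to 450, post-dose QTcF 501 to 509 and heart rate 61 bpm or more. With (b) rewritten as QTcF ≥ 500, none remain. That must be so: QTcF above 500 implies QTcF at least 500, and a rise above 60 implies a rise of at least 60.

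**The case against.** The best reply is that nobody will read the text literally. The features that show it is a slip (QTc-judged repeats, QTcF referral, the closing paragraph) also tell site staff what is meant. Section 7.1.1 acts on its own, on the average of three tracings, so no participant escapes withdrawal and two more ECGs add little confirmation.

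Other safeguards remain. Under 7.1.1 the ECG review is documented, and "Any new clinically relevant finding should be reported as an AE". Under 8.3.3, "the investigator is required to proactively follow each participant at subsequent visits/contacts", and Appendix 3 provides for supplemental measurements when medically indicated. The third route to continuous monitoring is on QTcF, the schedule of activities includes an early-termination ECG, and participants are confined throughout dosing. The band is thin, about 12 people are enrolled, and Protocol 2.2.4.1 reports no clinically meaningful ECG findings in the first-in-human study.

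All of this stands, and it limits the importance of the point. It does not make the rule correct: the literal text drops a mandatory monitoring series in cases where withdrawal is mandatory. The first-in-human ECG data also come from PF-07321332 with or without ritonavir, not with itraconazole added.

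A further objection is that 450 msec is an entry limit, whereas SAP 6.2.4 takes a new predose baseline in each period with no stated cap. That is right, but it cuts the other way. If a period baseline reached 460 or 470 msec, the missed QTcF values would run from 501 to 519 or from 501 to 529.

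**Conclusion.** The concern holds, at minor importance. Criterion (b) is on the wrong interval in both paragraphs of 8.2.3. That it is a slip for QTcF is an inference, though a well-supported one. On a literal reading, and with baseline QTcF no higher than 450 msec, the gap needs three things together: baseline above 440 msec, post-dose QTcF above 500 and less than 60 msec above baseline (so under 510), and heart rate above 60 × (QTcF/500)^3. Participants in the band are still withdrawn; they lose the mandatory confirmatory and hourly ECGs. The PK estimates, the sample size and the SAP's ECG summaries, which already use QTcF for the 500 msec limit, are unaffected.

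**What to change.** In both paragraphs of 8.2.3, put criterion (b) on QTcF at 500 msec or more. Leave the ≥ and > signs as they are.

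The QTcF-only wording has one cost: at slow heart rates an uncorrected QT of 500 msec or more with QTcF below 500 no longer triggers repeats by itself, unless (a) is met. At 50 bpm this concerns QT from 500 to about 531 msec (500 × (60/50)^(1/3) = 531.3), and at 55 bpm QT from 500 to about 515 msec (500 × (60/55)^(1/3) = 514.7). The bradycardia entry in Appendix 7 starts below 40 bpm and does not cover this range.

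If the sponsor wants to keep those repeats, the criterion can read QT or QTcF. This closes the gap without losing any present trigger. The text should then say which interval ends a series started by uncorrected QT, because the repeats are now judged on QTc.

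The change is a few words in two places, with no new scheduled procedures and no change to the analysis. It can go into the next protocol amendment; Protocol 10.1.1 requires IRB/EC approval before amendments that change the study design are implemented.

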8.2.4. Clinical Safety Laboratory Assessments

See [Appendix 2](#) for the list of clinical safety laboratory tests to be performed and the [SoA](#) for the timing and frequency. All protocol-required laboratory assessments, as defined in [Appendix 2](#), must be conducted in accordance with the laboratory manual and the [SoA](#).

Unscheduled clinical laboratory measurements may be obtained at any time during the study to assess any perceived safety issues.

The investigator must review the laboratory report, document this review, and record any clinically relevant changes occurring during the study in the AE section of the CRF.

Clinically significant abnormal laboratory findings are those which are not associated with the underlying disease, unless judged by the investigator to be more severe than expected for the participant's condition.

All laboratory tests with values considered clinically significantly abnormal during participation in the study or within 48 hours after the last dose of study intervention should be repeated until the values return to normal or baseline or are no longer considered clinically significant by the investigator or medical monitor.

If such values do not return to normal/baseline within a period of time judged reasonable by the investigator, the etiology should be identified and the sponsor notified.

See [Appendix 6](#) for suggested actions and follow-up assessments in the event of potential drug-induced liver injury.

8.2.5. COVID-19 Specific Assessments

Participants will be tested for SARS-CoV-2 infection by PCR prior to being admitted to the CRU for confinement and a subsequent SARS-CoV-2 test will be performed after 4 days (ie, upon completion of 4×24 hours in house), or if they develop COVID-19 like symptoms. Additional testing may be required by local regulations or by the Principal Investigator.

8.2.6. Pregnancy Testing

Pregnancy tests may be urine or serum tests, but must have a sensitivity of at least 25 mIU/mL. Pregnancy tests will be performed in WOCBP at the times listed in the [SoA](#). Following a negative pregnancy test result at screening, appropriate contraception must be commenced and a second negative pregnancy test result will be required at the baseline visit prior the participant's receiving the study intervention. Pregnancy tests will also be done whenever 1 menstrual cycle is missed during the active treatment period (or when potential pregnancy is otherwise suspected) and at the end of the study. Pregnancy tests may also be repeated if requested by IRBs/ECs or if required by local regulations. If a urine test cannot be confirmed as negative (eg, an ambiguous result), a serum pregnancy test is required. In such cases, the participant must be excluded if the serum pregnancy result is positive.

8.3. Adverse Events, Serious Adverse Events, and Other Safety Reporting

The definitions of an AE and an SAE can be found in [Appendix 3](#).

AEs may arise from symptoms or other complaints reported to the investigator by the participant (or, when appropriate, by a caregiver, surrogate, or the participant's legally authorized representative), or they may arise from clinical findings of the Investigator or other healthcare providers (clinical signs, test results, etc.).

The investigator and any qualified designees are responsible for detecting, documenting, and recording events that meet the definition of an AE or SAE and remain responsible to pursue and obtain adequate information both to determine the outcome and to assess whether the event meets the criteria for classification as an SAE or caused the participant to discontinue the study intervention (see [Section 7.1](#)).

During the active collection period as described in Section 8.3.1, each participant will be questioned about the occurrence of AEs in a nonleading manner.

In addition, the investigator may be requested by Pfizer Safety to obtain specific follow-up information in an expedited fashion.

